3.3 CONTROL DESCRIPTION: WAITLIST

Veterans randomized to the waitlist control condition will receive Whole Health STEPS after a 2 month wait. During the waitlist period, Veterans will not be prohibited from pursuing any treatment or services they deem appropriate, and healthcare utilization will be tracked through EMR record reviews. Veterans will be provided with information about available emergency and urgent mental health services, resources for social needs (e.g., homelessness), and other important resources to ensure that they are aware of how to engage support as needed.

Waitlist control was selected as the best option for the RCT to evaluate this service package because compared to designs with control groups where only one group receives Whole Health STEPS, it allows a more powerful test of Whole Health STEPS and it provides more feedback data to establish acceptability of the lower intensity interventions which are central to stepped care intervention design.

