1.2 SCHEMA

2 INTRODUCTION

2.1 STUDY RATIONALE

Functional impairment, limitation in social and occupational roles (Üstün & Kennedy, 2009), is a significant problem for Veterans. Across diagnostic categories, mental health symptoms are associated with functional impairment and difficulty with role-related task (Kazis et al., 1998; Löwe et al., 2008; Spitzer et al., 2006). Despite the availability of services, many Veterans with mental health symptoms do not engage in mental health treatment (Elbogen et al., 2013; Seal et al., 2010). ***Whole Health STEPS (Structured Tiered Engagement with Peer Support) is an innovative approach to engaging this population through combining two novel modalities to engage with Veterans, peer support and Whole Health, tailored for delivery in Primary Care Mental Health Integration (PCMHI) a platform designed to increase access to mental healthcare.***

This two phase pilot trial is designed to address two key objectives (1) evaluate the feasibility and acceptability of Whole Health STEPS and (2) evaluate the preliminary impact of Whole Health STEPS on patient outcomes.

- Phase 1 addresses objective 1 and will be an open trial (Eligible n=10) to test the feasibility of peer delivery in primary care and acceptability to Veterans to inform further manual adjustments. Feasibility of research procedures will also be evaluated to inform adjustments to the research protocol.
- Phase 2 addresses objective 2 and will be a pilot RCT with a waitlist control (Eligible n=44) to evaluate impact on functional impairment and feasibility for subsequent grant applications.

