3 STUDY DESIGN

3.1 OVERALL DESIGN

This study consists of a two phased clinical trial.

Phase 1 is an open trial establishing preliminary feasibility and acceptability of Whole Health STEPS and informing adjustments to the clinical manual. Participants will be followed for the duration of their participation in Whole Health STEPS, a period of approximately 2-3 months. Following phase 1 enrollment, the investigators will review the data, make adjustments to the Whole Health STEPS manual and research protocol as necessary, and proceed with enrollment in Phase 2.

Phase 2 is a 2-arm single-site pilot randomized clinical trial with a waitlist control evaluating Whole Health STEPS impact on patient outcomes and feasibility. Random assignment will be made by research staff following eligibility determination using a stratified permuted block design based on baseline functional impairment (mild-moderate functional impairment $IPF \leq 50$ vs. severe-extreme functional impairment $IPF \geq 51$). Participants will be followed for a period of approximately 4-5 months, 2-3 months will be participation in Whole Health STEPS and 2 months will be either be waitlist or follow-up depending on randomization outcome.

- Hypothesis 2a. Whole Health STEPS will demonstrate an effect size (d) > 0.3 on psychosocial functioning.
- Hypothesis 2b. Whole Health STEPS will demonstrate clinical feasibility including positive results on process outcomes, retention, fidelity, and appropriateness on stepped-care decision points.

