6.2 PARTICIPANT PAYMENT

Participants will be compensated at a rate of approximately \$20 per hour for research activities (i.e., interviews and self-report assessments). This compensation rate is the rate used for similar behavioral health clinical trials at the Syracuse VA and does not appear to lead to undue influence or coercion.

Compensation will occur through established VA payment procedures approved for research activities (e.g., direct deposit or via a VA debit card). Research staff will collect the minimum required identifiable information to properly process their payments (e.g., if research staff need bank account information to complete a direct deposit form, they will collect the necessary information for the form). Veterans will not be compensated for intervention appointments (i.e., Whole Health STEPS appointments with peers). The compensation for each of the study activities is detailed below.

Open Trial Study Activity	Estimated Burden	Compensation
Baseline Part 1 Consent & Eligibility Determination	~ 1 hour	\$20
Baseline Part 2 Remaining Assessments	~ 1 hour	\$20
Post Session Rating Forms (approximately 6 over the study)*	~ ¼ hour each *6 total = ~1.5 hours	\$5 each *6 total = \$30
Mid and Post Treatment Assessment	~1½ hour	\$30
Post Treatment Interview	~ ½ hour	\$10

* To reduce administrative burden with processing multiple payment vouchers for small amounts, the post-session rating forms will be paid in a lump sum at the end of the study along with the post-treatment interview payment unless participants request a different payment schedule.

RCT Study Activity	Estimated Burden	Compensation
Baseline Part 1 Consent & Eligibility Determination	~ 1 hour	\$20
Baseline Part 2 Remaining Assessments	~ 1 hour	\$20
Mid Assessment	~ 1 hour	\$20
Final Assessment	~ 1 hour	\$20
Post Treatment Assessment (added to either Mid or Final Assessment depending on randomization, or administered ASAP after a participant ends peer support services)	~ ½ hour	\$10
Post Treatment Interview	~ ½ hour	\$10

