11 DATA ANALYSIS PLAN

Qualitative feedback (e.g., interview responses and open-ended items) will be analyzed using a rapid qualitative analysis approach (Hamilton, 2013). Quantitative analyses for descriptive aims (e.g., fidelity, feasibility) will be analyzed using descriptive statistics (e.g., central tendency and spread statistics such as counts, means, ranges, and standard deviations). Quantitative analyses for patient outcomes will be analyzed using statistical modeling to establish effect size which will be evaluated in comparison with the a priori effect size of $d=.3$.

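### The waitlist's claimed power advantage does not hold for the randomised comparison against an untreated control, and the d judged against 0.3 is not tied to that comparison

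*Combined protocol and SAP*

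**What the plan says.** Section 3.3 gives two reasons for the waitlist. One is that it yields more feedback on acceptability. The other is power: "compared to designs with control groups where only one group receives Whole Health STEPS, it allows a more powerful test of Whole Health STEPS". The sentence locates the gain in the fact that both groups eventually receive STEPS.

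The same section states that "Veterans randomized to the waitlist control condition will receive Whole Health STEPS after a 2 month wait". Section 3.1 describes follow-up in which "2-3 months will be participation in Whole Health STEPS and 2 months will be either be waitlist or follow-up depending on randomization outcome". Section 6.2 lists a "Post Treatment Assessment (added to either Mid or Final Assessment depending on randomization", so one arm is expected to finish STEPS by mid and the other by final. No section dates the mid assessment in weeks or months from randomisation.

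Hypothesis 2a in Section 3.1 reads "Whole Health STEPS will demonstrate an effect size (d) > 0.3 on psychosocial functioning". Section 11 adds only that "Quantitative analyses for patient outcomes will be analyzed using statistical modeling to establish effect size", to be set against 0.3. Neither place says which groups, visits or time effects enter d.

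**The concern.** Treating the control arm later cannot sharpen a comparison made before that treatment starts. If later treatment is to add power, the waitlist arm's data after the wait must enter the analysis. The question is whether they add power while change over time is still controlled, or only when all change is credited to STEPS.

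Change over time is a realistic threat here. Under Section 4.1, IPF of at least 11 and a positive symptom screen are entry conditions. The Section 6 schedule collects those scales at Baseline Part 1, with no second pre-treatment IPF, so some regression to the mean is possible. Section 3.3 also leaves waitlisted Veterans free to use other services.

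At stake is the verdict on Hypothesis 2a, the only hypothesis about the primary patient outcome, in a phase meant to inform later grant applications. A randomised d and an uncontrolled pre-post d can fall on opposite sides of 0.3.

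**Working it through.** **Nothing to reproduce.** The power claim carries no number, and the Phase 2 size of 44 (Section 2.1) comes without alpha, power or model.

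**Inputs from the document.** 44 participants; d = 0.3; IPF at baseline, mid and final; waitlist arm treated after mid (inferred from Sections 3.1, 3.3 and 6.2).

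**Assumptions.** 1:1 allocation (Section 3.1 gives no ratio), so n = 22 per arm; SD 1; the same correlation ρ between any two visits, 0.5 to 0.7; a constant, persisting effect; two-sided 0.05; power = Φ(0.3/SE − 1.96).

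**1. Mid assessment only.** This is identical for a waitlist and for a control that is never treated.
- Unadjusted: SE = √(2/22) = 0.302, power about 17%.
- Baseline-adjusted: SE = √(2(1 − ρ²)/22) = 0.261 (ρ = 0.5) or 0.215 (ρ = 0.7), power 21% or 29%.

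**2. All three visits, time effects modelled.**
- Waitlist: variance = (2/22)·(1 − ρ)(1 + 2ρ)/(1 + ρ).
- Never-treated control: variance = (2/22)·(1 − ρ)(1 + 2ρ)/2.
- Ratio, waitlist to never-treated: 2/(1 + ρ), which exceeds 1 for every ρ below 1.

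| | ρ = 0.5: SE, power | ρ = 0.7: SE, power |
|---|---|---|
| Waitlist | 0.246, 23% | 0.196, 33% |
| Never-treated control | 0.213, 29% | 0.181, 38% |

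Over a wider range (ρ = 0.3 and 0.8) the order is the same: 19% against 26%, and 46% against 50%.

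**3. All three visits, time effects dropped.** The order reverses: 65% (waitlist) against 44% at ρ = 0.5, and 85% against 60% at ρ = 0.7. Under these assumptions, this is where the waitlist beats an untreated control.

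**4. Pooled pre-post change in all 44** (baseline to mid in the immediate arm, mid to final in the waitlist arm). SE = √(2(1 − ρ)/44) = 0.151 (ρ = 0.5) or 0.117 (ρ = 0.7).

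**5. Chance that d exceeds 0.3 when STEPS does nothing.** For pooled change this is 1 − Φ((0.3 − m)/SE), where m is natural improvement per interval in SD units. The document gives no value for m, so a range is shown.

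| m | ρ = 0.5 | ρ = 0.7 |
|---|---|---|
| 0 | 2% | 1% |
| 0.1 | 9% | 4% |
| 0.2 | 25% | 20% |
| 0.3 | 50% | 50% |

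For the randomised mid contrast, m cancels between arms:
- Unadjusted: 1 − Φ(0.3/0.302) = 16%.
- Baseline-adjusted: 1 − Φ(0.3/0.261) = 13% or 1 − Φ(0.3/0.215) = 8%.

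At m = 0.2 the excess for pooled change is therefore about 4 to 9 points over the unadjusted contrast and 11 to 13 over the adjusted one. At m = 0 or 0.1 there is no excess.

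**The case against.** A reader might infer that the sponsor intends to pool uncontrolled pre-post change and report it as the trial result. The document does not say so. Section 3.1 describes a two-arm randomised trial, which reads most naturally as a between-arm comparison, and no section proposes pooling. What stands is narrower: the power rationale needs such an analysis to hold against an untreated control, and the analysis text leaves the choice open.

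A reader might also infer that a waitlist can never help power. That goes too far in two respects. The sentence in Section 3.3 also covers active or attention controls, against which an untreated waitlist could show a larger difference; but the section does not give that reason. And later data need not be uncontrolled: a period-adjusted three-visit model gains a little over mid alone (23% against 21% at ρ = 0.5, 33% against 29% at ρ = 0.7). It still falls short of a never-treated control, so the criticism survives.

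Two further points stand. The size of any bias depends on natural improvement that the document does not quantify, and the IPF entry cut is low, so regression to the mean on IPF may be modest. The power sentence also does not drive the sample size, and the acceptability rationale supports the waitlist without it.

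**Conclusion.** The power statement in Section 3.3 is not correct for the randomised comparison against an untreated control of equal size. Precision is the same at mid, and power is roughly 5 to 6 percentage points lower with three visits and time effects modelled (ρ 0.5 to 0.7). The apparent advantage comes from ignoring change over time.

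The equality at mid needs only equal arm sizes in the two designs. The power and false-success figures rest on 1:1 allocation, equal correlations and no dropout; the three-visit figures also assume a constant, persisting effect, and the 20–25% assumes 0.2 SD of natural improvement.

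This should be fixed, but it does not undermine the choice of a waitlist. The correction is best made before outcome data are seen, because the choice of contrast can decide Hypothesis 2a.

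**What to change.** - **Sections 3.1 and 11:** define d for Hypothesis 2a as the baseline-adjusted between-arm difference in IPF at the mid assessment, in all randomised participants, with a 95% CI.
- **Timing:** state when mid occurs. A 2-month wait and a STEPS period of 2–3 months do not fit together as written: a mid visit at 2 months may precede completion of STEPS, and one at 3 months may follow the start of STEPS in the waitlist arm. The passages must be reconciled so that mid precedes any waitlist participant starting STEPS; which period to alter is for the investigators.
- **Secondary results:** report waitlist-phase change, pooled pre-post change and the immediate arm's follow-up as secondary and uncontrolled, and do not compare them with 0.3. A period-adjusted three-visit model may be a secondary analysis, with its assumption of a persisting effect stated.
- **Section 3.3:** delete or qualify the power claim and keep the acceptability rationale.

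The cost is protocol and SAP wording, plus the loss of a favourable power statement.

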3.4 FIDELITY & PEER STAFF QUALIFICATIONS

Peer staff may include Syracuse VA peer support specialists/apprentices, Syracuse VA or CIH staff employed in other roles who have appropriate peer qualifications, and/or peer support specialists/apprentices from other VA sites with whom we have active research or clinical partnerships (e.g., Palo Alto, Pittsburgh, Houston). Peers will have received training in peer support through a training program approved by the PI (e.g., the VA or New York State Peer Certification program) and will receive additional training in Whole Health STEPS procedures including training in Whole. Peer training in Whole Health STEPS will include training techniques such as reading materials (e.g., reviewing the manual) and structured practice (e.g., role plays). Peers will also receive ongoing supervision from the PI or another qualified peer supervisor to review ongoing cases and provide additional follow-up training as needed.

Intervention fidelity will be evaluated through a fidelity checklist developed specifically for Whole Health STEPS.

3.5 STUDY INTERVENTION/EXPERIMENTAL MANIPULATION ADHERENCE

Participant adherence to Whole Health STEPS will be tracked through peer documentation of appointment attendance and research staff documentation of retention (i.e., intervention and research withdrawal and/or lost to follow-up). Intervention retention will be evaluated through the percentage of Veterans who complete Whole Health STEPS. Completion is defined as either (1) continued engagement

with the peer specialist throughout the Whole Health STEPS phase as indicated by continuing to respond affirmatively to peer outreach efforts AND/OR (2) planned termination of Whole Health STEPS because the Veteran has made successful progress.

4 STUDY POPULATION

4.1 INCLUSION CRITERIA

To be eligible to participate in this study, an individual must meet all of the following criteria:

Inclusion Criteria	Operational Definition
1. Veteran status	Designated as a Veteran in the EMR
2. Age 18 or older	Age 18 or older in the EMR as of the date of enrollment
3. Enrolled in primary care at the Syracuse VA Medical Center or affiliated Community-Based Outpatient Clinic	Primary care clinic and/or Primary care provider in EMR are affiliated with Syracuse VAMC or CBOC
4. Have at least mild functional impairment	Inventory of Psychosocial Functioning (IPF \geq 11)
5. Screen positive on at least one primary care mental health screener	PHQ-9 \geq 10, PCL-5 \geq 31 AND a qualifying event on the LEC, GAD-7 \geq 8, and/or AUDIT \geq 8 for men/ \geq 7 for women

4.2 EXCLUSION CRITERIA

An individual who meets any of the following criteria will be excluded from participation in this study:

Exclusion Criteria	Operational Definition
1. Actively engaged with an equivalent or higher level of care with the exception of medication management for mental health concerns	Pending or planned future appointments in: 
 Whole Health Coaching/Peer Support or other individual coaching/support for health, wellness, or lifestyle changes PCMH Outpatient psychotherapy Peer support
2. Preference for direct referral to mental healthcare	Veteran answers affirmatively to the question "Would you prefer a referral for mental health services rather than participate in this trial?"
3. Recent changes to psychotropic medications	Change in medication type or dose within the last 2 months to a psychotropic medication or a medication prescribed for mental/behavioral health concerns
4. Severe impairment preventing engagement with a peer, warranting direct referral to a licensed independent provider for monitoring	
 High risk based on the P4 screener, and/or Significant cognitive impairment (BOMC $>$ 10), and/or

and follow-up, and/or affecting ability to complete research tasks.	
 • Need for accommodations that would invalidate research measures, and/or • Inability to sustain attention/concentration to complete questionnaires, interviews, and/or peer sessions, and/or • Other significant concerns about impairment.
5. Inability to independently communicate in verbal and written English	Demonstrates inability to understand and respond to research interviews and self-report assessments during the baseline in English, without assistance from a translator or interpreter.

5 RECRUITMENT PLAN

To recruit this sample, we intend to use direct marketing and/or referrals from the primary care team. Direct marketing could include a number of different strategies including posting paper flyers/brochures at VA and community locations (e.g., the Vet Center, ClearPath for Veterans, etc.), posting electronic flyers on electronic platforms (e.g., the VA television screens, VA facebook site), and tabling at the VA Medical Center and community events. Primary care team referrals will be facilitated by informational flyers and brochures, personal communication, and/or presentations at staff meetings. We will also conduct targeted chart reviews and electronic medical record datapulls to help providers identify potentially eligible Veterans and facilitate referrals. For recruitment purposes, the following criteria will be used to identify Veterans from medical records using a case finding procedure or the VA Informatics and Computing Infrastructure (VINCI):

- Veteran status
- Age 18 or older
- Enrolled in primary care at the Syracuse VA or an affiliated clinic based on primary care services at one of the aforementioned locations
- Positive behavioral health screen (i.e., PHQ-9, PHQ-2, PC-PTSD-5, PCL-5, GAD-7, AUDIT, or AUD-C) or relevant mental health diagnosis (i.e., depression, anxiety, PTSD, hazardous alcohol use) on the same day as a recent primary care encounter
- No recent (i.e., last month)¹ or pending peer support, Whole Health Coaching, PCMHI, or psychotherapy appointments.
- No recent (i.e., past two months) changes in dose or type of psychotropic medications
- No high risk suicide flags in the last year or positive suicide screens (i.e., C-SSRS, PHQ-9 item #9) within the last month
- Diagnosis of dementia within the last year

Contact information and identifying information (i.e., name, address, phone number, SSN) will be accessed to allow research staff to verify EMR information and contact potential participants.

¹ Although recent appointments are not part of the exclusion criteria, Veterans with recent appointments are not included in the electronic medical records recruitment pool to reduce recruitment of Veterans who may be pending scheduling their next appointment with an established provider. If Veterans are referred from other sources who have recent appointments of these types, they will be eligible as long as they meet the inclusion/exclusion criteria including no pending appointments.

Demographic information (including race, ethnicity, gender/sex) will also be accessed to allow staff to recruit a diverse population and increase recruitment efforts to Veterans from under-represented groups as needed.

For initial recruitment, Veterans identified through medical records will first be sent a recruitment packet (including a personalized invitation letter, study brochure, and informed consent information) then research staff will make multiple attempts to reach Veterans by the phone to conduct a phone screen. Veterans who are referred directly from a provider (e.g., warm handoff) or who contact the study through direct marketing (e.g., called the phone number on a flyer) will be given the option to complete the phone screen immediately and will be mailed information as soon as practical after initial contact. For all participants, an initial screening will be conducted to determine appropriateness of a baseline interview. Format of the screening (in person or telephone) will be determined based on Veteran preference and relevant safety-guidelines for in person meetings.

As appropriate, we will share names of Veterans we determine to be ineligible prior to contact with other studies approved to recruit using the same datapull procedures with overlapping eligibility criteria (e.g., if a participant schedules an appointment which would make them ineligible for our study after the datapull before recruitment, but that participant would otherwise be eligible for another study approved to access the name through the same means) we will share that information.

See [1.2 Schema](#) for the anticipated number of Veterans to be screened for the target enrollment.

6 ASSESSMENT PLAN

Assessments will be conducted with Veterans in person, over the phone, or electronically using Qualtrics or REDCap (Research Electronic Data Capture) depending on format of the assessment, safety guidelines for in person meetings, and Veteran preference. Electronic data collection will be the primary data collection strategy but as a contingency plan if electronic administration is not feasible, staff will make every effort to collect the data in an alternate format (paper or oral format) to reduce data loss. If paper format is used, it will be returned in person or via pre-paid envelope. Research staff will call, text using a VA iPhone and/or send an SMS text via Qualtrics or REDCap, and/or send e-mails via a no-reply, Qualtrics or REDCap generated email address to remind participants to complete assessments as needed. See [Data Security Plan](#) for Qualtrics and REDCap security information. Email and text reminders will follow current VA guidance on information security procedures for these communication methods. If oral format is used, it will be through phone, VA approved video-conferencing format, or in person. As a safety precaution, when conducting assessments virtually, research staff will also confirm a phone number for call back, a physical address for where the Veteran is at that moment, an emergency contact person/phone number in case the Veteran has a medical or mental health emergency while on the phone, and two identifiers to confirm the Veteran's identity.

Electronic medical records data collection will be facilitated by research staff with recruitment activities occurring monthly and outcome data collection occurring at the end of the trial. Upon initial recruitment screening, baseline interviews will be scheduled to review consent and HIPAA information and to determine eligibility. If the Veteran chooses to participate in the study and appropriately answers comprehension questions, research staff will document verbal consent on the approved verbal informed consent script. This modification will reduce burden on participants by eliminating the requirement to travel for a baseline assessment to administer written consent and increase the feasibility of the research trial by broadening the population who will be able to participate.

After obtaining verbal consent, research staff will administer the following assessments at the specified timepoints:

Construct/ Function	Assessment	Recruitment Admin Data	Baseline Part 1	Baseline Part 2	Each Session or Post-Session	Mid Assessment	Final Assessment	Post-Treatment*	Post-Study Admin Data
Sample Description, Recruitment, & Screening	EMR Patient Identifiers and Contact Information	X							
	Self-Report Contact Information		X						
	EMR Demographics	X							
	EMR Mental Health Screeners & Relevant Diagnoses	X							
	EMR Veteran Status	X							
	EMR Primary Care Team Information								
	EMR Medications	X							
	EMR Problem List	X							
	BOMC (for cognition/ orientation)		X						
	P4 Screener (for suicidality)		X						
	Preference for direct referral to behavioral health		X						
	Demographics Questionnaire			X					
Psychosocial Functioning (Primary Patient Outcome)	IPF (psychosocial functioning)		X			X	X		
Behavioral Health Symptoms	PHQ-9 (depression)		X			X	X		
	GAD-7 (anxiety)		X			X	X		
	LEC (PTSD)		X						
	Criterion A Assessment (PTSD)		X						
	PCL-5 (PTSD)		X			X	X		
	AUDIT (alcohol use)		X			X	X		
Other Peer Services Outcomes	EMR VA Healthcare and Social Services Appointments	X							X
	Self-Report non-VA Healthcare and Social Services Utilization		X			X	X		
	RAS-SF (recovery)			X		X	X		

	WAI (therapeutic relationship)							X	
Other Whole Health Outcomes	MILM (meaning in life)			X		X	X		
	QOLI (quality of life)			X		X	X		
	ACORN (resources)			X		X	X		
	WHGAT (Whole Health Goal Attainment)				X				
Whole Health STEPS Feasibility	Intervention retention								X
	Fidelity Checklist				X				X
	Peer Post-session feedback forms (also falls under acceptability)				X				
	Supervisor Post-session feedback forms (design/manual usability)				X				
	UE-ATR (safety)								
Whole Health STEPS Acceptability	Veteran post-session feedback forms				X				
	Veteran post-treatment feedback interview							X	
	CSQ (satisfaction)							X	
Research Feasibility	Recruitment and eligibility rates								
	Data Collection & Procedural Problems								
	Research retention								X

Notes. Assessments in bold are included in eligibility determination. Assessments in italics are for the open trial phase only. The post-treatment assessments are added to either the mid or final assessment as appropriate in the RCT phase. If a participant ends peer support services earlier than expected before the mid or final assessments are due (e.g., due to withdrawal from intervention but not research, because their goals were met with fewer sessions), the post-treatment will be administered at the participant's earliest convenience separately from the mid or final assessments.

